7. ASSESSMENTS

All study related assessment will be performed after obtaining informed consent document, and assent as appropriate.

7.1. Parasite Clearance Assessments

The primary tool for assessing the parasitological clearance is the peripheral blood smear (thick and thin), which will be prepared at the study sites with the standard Giemsa staining for parasite identification and count using white blood cell counting method on thick smears. Each blood smear will be read by two microscopists in a blinded fashion (blinded to the reading of other microscopists). In the event of discrepancy, the slide will be read by third microscopist and parasite density will be calculated by averaging the two most concordant counts. All the smears will be preserved for possible third party confirmation. Refer to the Laboratory Manual for details. If and when the blood smears become positive after initial parasite clearance, the blood blot collected at that visit will be tested for molecular genotyping assays to differentiate the recrudescence from reinfection.

- Recrudescence: Reappearance of asexual *P. falciparum* blood stage parasites confirmed by the results of molecular testing. This finding reflects that the subject failed the treatment since the original parasite recurred;
- Reinfection: Infection by a different genotypic parasite as documented by molecular testing. This finding reflects that the subject did not fail treatment since a molecularly distinct parasite was found at the time of recurrence.

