cost to *P. falciparum*.⁷²⁻⁷⁴ Kenya recently reported similar micro-evolutionary changes in *P. falciparum* since suspending CQ use in 1999, but at a slower rate than Malawi. Many reasons may contribute to delayed return of sensitivity, not the least of which is that CQ continued to be widely available for four years after the national treatment policy was changed, and the fact that amodiaquine, an analogue of CQ, was the second-line treatment during the CQ era and continues to be used to this day as the second-line therapy.⁷⁵

Evidence of CQ efficacy was reported, as well, in a recent four-arm clinical trial conducted in Ghana among pregnant women with asexual *P. falciparum* stage parasitemia. Women randomized to a CQ treatment group (N=225) received 600 mg for 2 days and 300 mg on the third day. The Day 28 treatment failure rate (PCR uncorrected) was 30% (62 of 208). Polymerase chain reaction (PCR) analysis confirmed that 14% (30 of 208) were true treatment failures (recrudescence) while 6% (11 of 208) were re-infections. PCR was unable to distinguish cases of recrudescence from new infection in the remaining 10% (21 of 208).¹⁴ In a phase 2 treatment trial in India (066-191), CQ were given to patients with smears positive for *P. falciparum* at dose of CQ base 600 mg for first two days and 300 mg on the third day. The analysis indicated suboptimal efficacy (27% at Day 28) with CQ monotherapy.⁵³

In addition, CQ may offer protection against maternal-to-child transmission (MTCT) of HIV. Cord blood containing high levels of CQ has been associated with a reduced risk of MTCT of HIV.⁷⁶ Viral shedding in breast milk has been lowered among HIV-positive women who received three days of 600 mg CQ as an anti-malarial chemoprophylactic.⁷⁷ It is unknown whether this reduction in viral load is sufficient to prevent HIV transmission among mothers who choose to breastfeed.

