9.2.1. Analysis of Primary Endpoint

The proportion of subjects with parasitological response (PCR corrected) at Day 28 post first dose of study medication will be estimated for the primary endpoint using the MITT and PP subject populations. The proportion will be estimated from the Kaplan-Meier curve based on the time to the first occurrence of parasitological failure (PCR corrected). Use of the Kaplan-Meier curve/product limit estimator is recommended by WHO⁸ and has been used in analyzing primary efficacy endpoints in late stage antimalarial treatment clinical trials.⁹²⁻⁹⁴

A subject will be a parasitological responder if she has a zero parasite count on the Day 7 visit without subsequent recrudescence (PCR corrected) through the day of consideration, otherwise she is a parasitological failure. In addition, subjects who withdraw from the study treatment during the first three days due to development of malaria symptoms and are administered antimalarial standard of care treatment for malaria in pregnancy, will be considered parasitological failures. The time (number of days) to the first occurrence of parasitological failure will be the analysis variable. The time in days is defined as [date of the parasitological failure event – date of the first dose of study medication + 1].

Subjects who do not experience the defined event (parasitological failure) will be censored as follows:

- Subjects who withdraw from the study early due to any reason will be censored on the day of the last available blood smear measurement;
- Subjects who continue on in the study but have all remaining blood smears missing from a given point in time onward will be censored on the day of the last available smear;
- Subjects completing the Day 42 visit post first dose of study medication will be censored on the day of the last available blood smear measurement;
- Subjects receiving any concomitant antimalarial for reinfection (PCR corrected) or in the absence of parasitemia will be censored at the visit date if the antimalarial is given after collection of the blood smear on that day. Otherwise the subject will be censored on the day of the last available previous blood smear measurement;
- Subjects who are lost to follow-up without any follow-up blood smears will have a censored duration of 1 day.

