The proportion of subjects with parasitological response (PCR corrected) at Day 28 (primary) will be estimated from the Kaplan-Meier curve and its standard error estimated by the Greenwood formula. If less than 100%, a two-sided 95% confidence interval for the estimated proportion of subjects with parasitological response will be computed.

Additional sensitivity analyses will also be performed using the MITT and PP subject populations. The sensitivity analyses will consider premature discontinuation due to any reason as parasitological failure, if not already a parasitological failure due to a defined event. The same statistical methods will again be used to estimate the proportion of subjects with parasitological response (PCR corrected) at Day 28.

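### After a zero Day 7 count, a recurrence with an unresolved genotype stays event-free under Sections 7.1 and 9.2.1, which can raise the PCR-corrected primary rate

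*Protocol*

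**What the plan says.** Protocol Section 7.1 sorts parasites that reappear after clearance into two classes. Recrudescence is the return of "blood stage parasites confirmed by the results of molecular testing". Reinfection is "Infection by a different genotypic parasite as documented by molecular testing". Both need a molecular result, and no third class is given.

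Protocol Section 9.2.1 sets the condition for response in these words: "zero parasite count on the Day 7 visit without subsequent recrudescence (PCR corrected) through the day of consideration, otherwise she is a parasitological failure". It adds one further failure route, which needs no genotype: "subjects who withdraw from the study treatment during the first three days due to development of malaria symptoms", when standard antimalarial treatment is given.

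The same section lists five censoring rules. The one on antimalarial use reads: "Subjects receiving any concomitant antimalarial for reinfection (PCR corrected) or in the absence of parasitemia will be censored at the visit date", with the previous smear used if the drug came before that day's smear. A woman without an event who completes Day 42 is censored at her last smear.

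On robustness, Section 9.2.1 says: "The sensitivity analyses will consider premature discontinuation due to any reason as parasitological failure". Section 9.2.2 repeats the analyses on PCR-uncorrected results, and Day 28 is among the uncorrected time points in Section 2.2.

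Section 1.4.2.2 gives a genotyping breakdown from the chloroquine arm of a trial in pregnant women in Ghana. There, "PCR was unable to distinguish cases of recrudescence from new infection in the remaining 10% (21 of 208").

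**The concern.** A blot that does not amplify, is missing or cannot be classified puts a recurrence in neither class of Section 7.1. The responder rule in Section 9.2.1 nevertheless gives an answer for it: without a confirmed recrudescence there is no failure, so the woman remains a responder. If she is then treated for that recurrence, the treatment is neither for a PCR-identified reinfection nor given in the absence of parasitaemia. The antimalarial censoring rule therefore does not remove her, and clean smears produced by another drug extend her event-free time.

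What is at stake is the direction of the default. An unresolved laboratory result counts towards the drug's success, and poorer genotyping gives a higher primary rate. The confidence interval does not reflect this. The study is open label and single arm, so there is no control group in which the same default would operate and partly cancel.

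**Working it through.** **Step 1. Apply the text to each kind of recurrence after a zero Day 7 count.**

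| Genotype at recurrence | Failure event (7.1 with 9.2.1) | Named in the antimalarial censoring rule | Status in the primary analysis |
|---|---|---|---|
| Recrudescence confirmed | Yes | Not needed | Failure |
| New infection documented | No | Yes | No event; censored if treated |
| Indeterminate, failed or missing | No | No | Event-free to the last smear, treated or not |

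**Step 2. Reproduce the protocol's own breakdown (Section 1.4.2.2, n = 208).**

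- Recrudescence: 30/208 = 14.4% (printed 14%).
- Reinfection: 11/208 = 5.3% (printed 6%).
- Unresolved: 21/208 = 10.1% (printed 10%).
- All recurrences: 30 + 11 + 21 = 62, and 62/208 = 29.8% (printed 30%).
- Unresolved share of recurrences: 21/62 = 33.9%.

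**Step 3. Day 28 corrected success in those 208 women, by handling rule.**

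| Unresolved cases treated as | Calculation | Success | Literal rule is higher by |
|---|---|---|---|
| Responses (literal rule) | (208 − 30)/208 = 178/208 | 85.6% | – |
| Excluded | (187 − 30)/187 = 157/187 | 84.0% | 1.6 points |
| Split 30:11 | 21 × 30/41 = 15.4 added failures; (208 − 45.4)/208 | 78.2% | 7.4 points |
| Failures | (208 − 51)/208 = 157/208 | 75.5% | 10.1 points |

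The literal rule gives the highest figure of the four. This step shows direction only. The data are from chloroquine alone.

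**Step 4. Scale to this trial.**

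- Section 9.1 plans about 166 women with about 10% dropout: 166 × 0.90 = 149.4, so about 149 evaluable. Treating the Kaplan-Meier estimate as a simple proportion, one unresolved case moves the rate by 1/149 = 0.67 points.
- Section 1.5.2.2 gives uncorrected Day 28 rates of 95% and 99% for azithromycin plus chloroquine in two adult studies. That puts failures from any cause, and hence recurrences, at up to 5% and 1%.
- The documents give no genotyping failure rate for this trial. As an assumption, take 10% to 34% unresolved, the upper end being the Ghana share.
- Low end: 0.10 × 1 point = 0.1 points. High end: 0.34 × 5 points = 1.7 points. In women, 0.001 × 149 = 0.15 and 0.017 × 149 = 2.5, so from fewer than one to two or three.

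**Step 5. Cross-check from the corrected-minus-uncorrected gap.** The same studies reported corrected rates of 98% and 100%, so the gaps are 98 − 95 = 3 points and 100 − 99 = 1 point. Applying 10% to 34% gives 0.10 × 1 = 0.1 to 0.34 × 3 = 1.0 points. If the whole gap were unresolved cases, the shift would be 1 to 3 points. This bound assumes that those studies did not already score unresolved cases as failures, which the documents do not say. Those women and men were also non-pregnant adults, whereas this trial enrols primigravidae and secundigravidae.

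**The case against.** The strongest reply is that the protocol never says an unresolved recurrence is a response. Section 7.1 is symmetric: reinfection also needs molecular documentation, and the stated reason a reinfected woman has not failed is that a distinct parasite was found. On that sentence an unresolved case has not earned non-failure either. Section 9 leaves detailed methods to an analysis plan that was not available here, and rules for unclassifiable laboratory results are often placed there. This stands in part. The scoring is an inference from the definitions, and a reader should not report it as an explicit rule. But Section 9.2.1 is more than silent: its responder rule, followed as written, yields the favourable answer. The protocol has also fixed the endpoint and its censoring itself, and Section 9 requires major changes to the primary endpoint definition or analysis to appear in an amendment.

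Second, the PCR-uncorrected Day 28 analysis is already planned and counts every recurrence as a failure, so readers will see a lower bound beside the primary result. That is true and limits the harm. It does not isolate the unresolved cases, because it fails true reinfections too.

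Third, counting all unresolved cases as failures brings a bias of its own. In the Ghana data it gives 75.5%, which is 78.2 − 75.5 = 2.7 points below the 30:11 split. This also stands, and it is why the alternative handling belongs in a sensitivity analysis.

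Fourth, no hypothesis is tested, and the likely shift is small beside the 5-point half width in Section 9.1. That limits the consequence without supporting a default in the drug's favour.

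**Conclusion.** The point holds in this form: after a zero Day 7 count, an unresolved recurrence is event-free under the literal text and, if treated, escapes the antimalarial censoring rule. Relative to counting it as a failure, this can only raise the primary rate. The expected size is about 0.67 points per case, and roughly 0.1 to 1.7 points in all. That range rests on the assumed 10% to 34% unresolved share and on a recurrence rate carried over from adult studies.

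Three stronger readings are tempting and are not supported:

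- That molecular confirmation is the only route to failure. Day 7 non-clearance and early treatment withdrawal for malaria symptoms are failures without it.
- That the AZCQ rate is inflated by 10 points. That gap comes from chloroquine monotherapy with about 30% uncorrected failure, and it compares the literal rule with the most severe alternative.
- That unresolved genotypes are common in pregnancy as such. The protocol reports one arm of one trial and does not attribute the result to pregnancy.

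**What to change.** In Section 9.2.1, state that only a genotype-confirmed new infection is handled as reinfection. State also that a recurrence after clearance with an indeterminate, failed or missing genotype does not remain a response: in the PCR-corrected primary analysis it is a failure dated at the positive smear. Add a sensitivity analysis that censors these women at their last negative smear. Failure or censoring as the primary rule is a choice, so both results should be reported. Settle this before the early analysis that follows the last Day 42 visit.

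The cost is a short addition to Section 9.2.1 and one extra analysis, with no new data. The reported rate may be slightly lower, and some true reinfections will count as failures in the primary analysis.

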7.2. Safety Assessments

Safety and tolerability will be assessed by spontaneously reported adverse events, history of concomitant treatments, temperature, hemoglobin concentrations, and EIU safety assessment according to Schedule of Activities.

- Spontaneous adverse events reporting: through Day 42. Refer to Section 8 (Adverse Event Reporting) for details;
- History of concomitant treatment assessment;
- Oral temperature through Day 42;
- Hemoglobin levels: with HemoCue™, via finger stick or peripheral blood collection) at baseline and on Day 42.
- EIU Assessments:

Every attempt should be made to follow up the subject after the delivery for EIU assessment. In case of no associated serious adverse events (SAE), subjects should be followed up by fieldworkers at clinic or at home within 14 calendar days after expected date of delivery or termination of pregnancy.

- Maternal information and delivery: any history of complications during pregnancy, at and after delivery, eg, pre-eclampsia, hemorrhage, infection, etc.
- Neonatal information:
 - Outcome of pregnancy:
 - Full term live birth;
 - Premature live birth;
 - Still birth;
 - Spontaneous abortion/miscarriage;
 - Induced or elective abortion;
 - Gestational age at birth.
 - Outcome of infant:
 - Normal neonate;
 - Congenital malformation/anomaly;
 - Other neonatal problem/abnormality: include dysmaturity, neonatal illness, hospitalization, drug therapies.

Infant details: include sex, weight at birth, length at birth, head circumference at birth, APGAR scores (1/5 minutes).

- Fetal information will be collected in the event of pregnancy termination.
- Additional information and further follow-up on the neonate will be conducted when feasible and relevant to the assessment of the case if applicable.

7.3. Pharmacokinetic Assessments

Blood samples will be collected from the subjects who consented for PK assessments. Followings are the sampling time points:

090177e1811d3ccb\Approved\Approved On: 19-Feb-2010 20:59

- Day 0 prior to dosing of AZCQ (window: -1 to 0 hour); collect blood samples for determination of AZ, CQ, and desethyl-CQ concentration;
- Day 2: prior to dosing of AZCQ (window: -1 to 0 hour), 2 hours (as close to 2 hours as possible) and 8 hours (window: 4 to 12 hours) post dose, as feasible; collect blood samples for determination of AZ, CQ, and desethyl-CQ concentration;
- Days 7, 14, 21 and 28: a random time point during the visits; collect blood samples for determination of AZ, CQ, and desethyl-CQ on Days 7 and 14; collect blood samples only for determination of CQ and desethyl-CQ concentration on Days 21 and 28.

Actual sampling date and time should be recorded for all samples. Subjects who received even one dose will be followed up for all subsequent PK sample collection.

7.3.1. Serum for Analysis of Azithromycin

Blood samples (3 mL) to provide a minimum of 1 mL serum for pharmacokinetic analysis of AZ will be collected into appropriately labeled tubes containing no preservative or anticoagulant or serum separator at protocol-specified times (See Section 6.1). All efforts will be made to obtain the PK samples at the exact nominal time relative to dosing. However, samples obtained within 10% of the nominal time (eg, within 6 minutes of a 60 minute sample) from dosing will not be captured as a protocol deviation, as long as the exact time of the sample collection is noted on the source document and data collection tool (eg, CRF).

The whole blood samples will remain at room temperature until clotted (for approximately 30 minutes). Samples will be centrifuged at approximately 1700 x g for about 10 minutes at 4°C. The serum will be transferred into appropriately labeled screw-capped polypropylene tubes and stored at -20°C within 1 hour of collection until shipment for assay. Samples from each individual subject will be stored in a package for that subject.

Samples will be analyzed for AZ concentrations using a validated analytical method in compliance with Pfizer standard operating procedures. Samples may be used for further evaluation of the bioanalytical method. These data will be used for internal exploratory purposes and will not be included in the clinical report.

7.3.2. Plasma for Analysis of Chloroquine and Desethyl-Chloroquine

Blood samples (4 mL) to provide a minimum of 2 mL plasma for PK analysis of CQ and desethyl-CQ will be collected into appropriately labeled tubes containing K3EDTA at protocol-specified times (See Section 6.1). All efforts will be made to obtain the PK samples at the exact nominal time relative to dosing. However, samples obtained within 10% of the nominal time (eg, within 6 minutes of a 60 minute sample) from dosing will not be captured as a protocol deviation, as long as the exact time of the sample collection is noted on the source document and data collection tool (eg, CRF).

Specimens will be centrifuged at approximately 1700 x g for about 10 minutes at 4°C. The plasma will be transferred into appropriately labeled screw-capped polypropylene tubes and stored at -20°C within 1 hour of collection until shipment for assay. Samples from each individual subject will be stored as a package for that subject.

Samples will be analyzed for determination of CQ and desethyl-CQ concentrations using a validated analytical method in compliance with Pfizer standard operating procedures. Samples may be used for further evaluation of the bioanalytical method. These data will be used for internal exploratory purposes and will not be included in the clinical report.

7.3.3. Shipment of Pharmacokinetic Samples

The shipment address and assay lab contact information will be provided to the investigator site prior to initiation of the study.

8. ADVERSE EVENT REPORTING

8.1. Adverse Events

All observed or volunteered adverse events regardless of treatment group or suspected causal relationship to the investigational product(s) will be reported as described in the following sections.

For all adverse events, the investigator must pursue and obtain information adequate both to determine the outcome of the adverse event and to assess whether it meets the criteria for classification as a serious adverse event requiring immediate notification to Pfizer or its designated representative. For all adverse events, sufficient information should be obtained by the investigator to determine the causality of the adverse event. The investigator is required to assess causality. For adverse events with a causal relationship to the investigational product, follow-up by the investigator is required until the event or its sequelae resolve or stabilize at a level acceptable to the investigator, and Pfizer concurs with that assessment.

8.2. Reporting Period

For serious adverse events, the reporting period to Pfizer or its designated representative begins from the time that the subject provides informed consent, which is obtained prior to the subject's participation in the study, ie, prior to undergoing any study-related procedure and/or receiving investigational product, **through Day 42 and including 39 calendar days after the last administration of the investigational product, or until one month after the delivery or the termination of pregnancy (which ever is later)**. If pregnancy outcome meets the classification as a serious adverse event, it will be reported accordingly as serious adverse event (refer to Section 8.9 for details). Any serious adverse event occurring any time after the reporting period must be promptly reported if a causal relationship to investigational product is suspected.

Adverse events (serious and non-serious) should be recorded on the CRF from the time the subject has taken at least one dose of study treatment through last subject visit.

